7 STATISTICAL ANALYSIS

7.1 General

Smith & Nephew's Global Biostatistics group will conduct the statistical analysis for this study. Unless otherwise stated, all significance tests and hypothesis testing will be two-sided, performed at the 5% significance level. Resulting p-values will be quoted and 95% two-sided confidence intervals will be generated where appropriate. All p-values will be rounded to three decimal places, p-values less than 0.001 will be presented as '<0.001' in all tables.

Baseline data, outcome variables and adverse events will be summarized according to the nature of the variable. Categorical and ordinal variables will be summarized with frequencies and percentages. Continuous variables will be summarized with the following summary statistics: number of observations, mean, median, standard deviation, minimum and maximum values. The outcome variables will be summarized for all recorded time points.

Appropriate parametric and/or non-parametric analyses will be chosen for statistical analysis. The analysis of continuous variables will be done using a paired-sample t-test if appropriate, to test for differences between the baseline and end of study outcomes. The Wilcoxon rank-sum tests will be explored if the data is non-normal.

If data allows, Kaplan-Meier estimates will be calculated for the survival data otherwise only the survival proportion with a 95% confidence interval will be reported..

All analyses will be performed in SAS version 9.4 (or later).

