This document contains information that is confidential and proprietary to Smith & Nephew PLC and Smith & Nephew, Inc. and is intended for use only by Smith+Nephew and its manufacturer. It shall not be reproduced or copied in whole or in part, nor shall the contents be disclosed by any means without prior written permission from Smith+Nephew, nor shall anyone make any use of it that is contrary to the expressed or implied wishes of Smith+Nephew.

Statistical Analysis Plan

Multicenter Clinical Observation Using the Cementless Version of the
POLARSTEM™

Number: D10070
ST: 1133
Version: 1.0, 30-Nov-2021
Page: 12 of 19

Public transportation	Yes, possible	1	
	No, unable	0	
Stairs	Normally without using a railing	4	
	Normally using a railing	2	
	In any manner	1	
	Unable to do stairs	0	
Socks/Shoes	With ease	4	
	With difficulty	2	
	Unable	0	
Range of Motion (ROM)	Flexion = FLEX+EXT-FLEX_ZERO	N/A	
	Movement = ABD+ADD-ABD_ZERO	N/A	
	Rotation = ER+IR-ER_ZERO	N/A	
ROM subscore	Flexion+Movement+Rotation		Range of Motion Domain (0 to 5)
	0 to 29	0	
	30 to 59	1	
	60 to 99	2	
	100 to 159	3	
	160 to 209	4	
	≥ 209	5	
Leg Length Difference (in mm)	None	N/A	
	Ipsilateral longer (LL_DIF_LONG)	N/A	
	Ipsilateral shorter (LL_DIF_SHORT)	N/A	
Absence of Deformity (AOD)	IF (FLEX_ZERO = . OR FLEX_ZERO < 31) AND (ABD_ZERO = . OR ABD_ZERO < 11) AND (ER_ZERO = . OR ER_ZERO < 11) AND LL_DIF_LONG < 33 AND LL_DIF_SHORT < 33 THEN AODScore = 4	0 or 4	Absence of Deformity Domain (0 to 4)
Total HHS		Sum of all domain scores per subject	Sum of all domain scores per subject

CONFIDENTIAL AND PROPRIETARY

This document contains information that is confidential and proprietary to Smith & Nephew PLC and Smith & Nephew, Inc. and is intended for use only by Smith+Nephew and its manufacturer. It shall not be reproduced or copied in whole or in part, nor shall the contents be disclosed by any means without prior written permission from Smith+Nephew, nor shall anyone make any use of it that is contrary to the expressed or implied wishes of Smith+Nephew.

Statistical Analysis Plan

Multicenter Clinical Observation Using the Cementless Version of the
POLARSTEM™

Number: D10070
ST: 1133
Version: 1.0, 30-Nov-2021
Page: 13 of 19

Note: The maximum possible score for the HHS is 100.			

For the WOMAC from HOOS, algorithms used in deriving the pertinent endpoints are as presented below.

WOMAC from HOOS Stiffness, Pain, and Physical Function Raw Scores			

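### The HHS scoring table credits a blank `*_ZERO` field as no deformity in the AOD rule but subtracts the same field in the ROM formulas, with no rule for what a blank means

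*SAP*

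**What the plan says.** All the rules at issue are in the Harris Hip Score table of SAP 7.4.

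- **ROM.** Three planes are defined: "Flexion = FLEX+EXT-FLEX_ZERO", "Movement = ABD+ADD-ABD_ZERO" and "Rotation = ER+IR-ER_ZERO". Their sum, "Flexion+Movement+Rotation", is banded into 0 to 5 points. No row covers a blank input or a missing sum. The band worth 4 points runs from 160 to 209, and the band worth 5 starts at 209.
- **AOD.** The condition opens "IF (FLEX_ZERO = . OR FLEX_ZERO < 31) AND (ABD_ZERO = . OR ABD_ZERO < 11" and ends "AND (ER_ZERO = . OR ER_ZERO < 11) AND LL_DIF_LONG < 33 AND LL_DIF_SHORT < 33 THEN AODScore = 4". A blank in any of the three `*_ZERO` fields therefore passes, just as a value under the cut-off does.
- **Total.** The four domain scores are added. The table does not say what happens when one is missing.

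Three other sections bear on this. SAP 7.1 states: "All analyses will be performed in SAS version 9.4 (or later". SAP 7.3 applies LOCF to missing outcome values but says nothing about blank items. SAP 7.11 summarises the HHS dimensions as well as the total, and tests preoperative against postoperative scores. SAP 7.4 also refers to each questionnaire's scoring instructions but reproduces none on blanks.

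**The concern.** The AOD rule shows that its authors expected blanks in these fields. The ROM formulas use the same fields as if they were always filled. In SAS, adding or subtracting a missing value gives a missing result, so the meaning of a blank decides which domain is wrong.

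- **Blank means 0 degrees.** AOD is right. ROM is lost for hips that had nothing to record, so the loss is selective. A lost postoperative total can be replaced by an older score under LOCF. A lost preoperative total has no earlier value to carry forward, so that hip leaves the paired test.
- **Blank means not examined.** A missing ROM is right. AOD gives full credit without evidence, and the AOD summary includes that credit even when the total is correctly missing.

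The leg-length part of the condition, "LL_DIF_LONG < 33 AND LL_DIF_SHORT < 33 THEN AODScore = 4", has a similar gap. SAS ranks a missing number below every value, so both comparisons are true when neither field is filled. A hip with no examination at all then scores 4 for AOD. Protocol 3.4 foresees telephone assessment of patients who do not attend. Whether such a contact creates an HHS record is not stated.

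**Working it through.** **The plan's own figure.** Function item maxima: 11 + 11 + 11 + 5 + 1 + 4 + 4 = 47. Total: pain 44 + function 47 + ROM 5 + AOD 4 = 100, which matches the stated maximum. The weights are sound; the problem lies only in blanks and band limits.

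**Illustrative hip.** These angles are assumed and are not in the documents: FLEX 120, EXT 10, ABD 40, ADD 30, ER 40, IR 30. Pain and function are at maximum (44 + 47 = 91), and leg length passes.

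With all `*_ZERO` fields recorded as 0, the planes are 120 + 10 − 0 = 130, 40 + 30 − 0 = 70 and 40 + 30 − 0 = 70. The arc is 270, ROM 5, AOD 4, and HHS 91 + 5 + 4 = 100.

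**Case 1: a blank means 0 degrees.** Same hip, with only `FLEX_ZERO` blank. The correct HHS is 100.

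| Coding | Arc | ROM | AOD | HHS |
|---|---|---|---|---|
| Plain addition and subtraction throughout | missing | missing | 4 | missing |
| As above, but total skips a missing domain | missing | missing | 4 | 91 + 4 = 95 |
| Arc skips the missing plane | 70 + 70 = 140 | 3 | 4 | 98 |
| Missing skipped inside each plane (SUM-type) | 270 | 5 | 4 | 100 |

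One true state gives missing, 95, 98 or 100, depending only on coding that the SAP leaves open. The last row is correct.

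**Case 2: a blank means not examined.** Take a true flexion value of 35 degrees, with EXT 0.

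- Recorded: 120 + 0 − 35 = 85; arc 85 + 70 + 70 = 225; ROM 5. AOD is 0 because 35 is not below 31. HHS = 91 + 5 + 0 = 96.
- Blank, plain addition: ROM and total are missing, which is right for an unexamined plane. AOD is still 4.
- Blank, missing skipped inside the plane: 120 + 0 = 120; arc 120 + 70 + 70 = 260; ROM 5; AOD 4; HHS 100, which is 4 points too high.

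With a true value of 20 degrees, the recorded arc is 100 + 70 + 70 = 240, ROM 5, AOD 4 (20 is below 31) and HHS 100. A blank gives the same AOD of 4. The credit is then unsupported but happens to be right.

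**No examination.** With the three `*_ZERO` fields and both leg-length fields blank, every part of the AOD condition is true in SAS, so AOD is 4.

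**Band limit.** An arc of exactly 209 meets both upper bands and scores 4 or 5, a difference of 1 point.

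**The case against.** The strongest reply is that only the AOD row is written as code. The ROM rows are arithmetic definitions. A programmer may set blanks to 0 first, or use a sum that ignores missing values, and if a blank means 0 degrees nothing is then mis-scored. The explicit test for a blank in the AOD row favours that meaning. This stands as far as it goes: one workable implementation exists. But the SAP does not state it, and the same coding produces the 4-point excess above if a blank means not examined.

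The CRF, which SAP 2 names as a related document, or the scoring instructions may settle the meaning. That is a reason to check them first. Even if they define a blank as 0, the ROM formulas still need to say so.

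On leg length, the SAS behaviour is helpful when a hip has a difference and only one of the longer and shorter fields is filled. That also stands, and the correction must not require both fields. It does not excuse a pass when nothing was recorded.

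Three stronger readings are tempting but not supported:

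- A reader might infer that the total is wrong whatever a blank means. The working shows two exceptions: blank as 0 with missing-tolerant summing (total 100), and blank as not examined with plain addition (total correctly missing).
- A reader might infer that a missing arc falls into the lowest ROM band. That band starts at 0, and a SAS missing value ranks below 0, so this happens only if the programmer drops the stated lower limit.
- A reader might infer a threat to the primary result, because SAP 4.1 lists HHS under the primary objectives. The primary endpoint in SAP 5.1 is survival, and SAP 5.2 makes HHS secondary.

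**Conclusion.** The inconsistency is real and should be corrected. Read literally, one of the two domain rules fails under either meaning of a blank, and a stated rule gives full AOD credit to a hip that was never examined. Whether the total HHS is affected depends on coding that the SAP does not specify.

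Per affected visit, the error is at most 5 points (ROM) or 4 points (AOD), or a lost total. The overlap at 209 adds a 1-point ambiguity at a single value.

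The effect on mean HHS cannot be computed. A reader might multiply 4 points by an assumed share of blanks and an assumed share truly deformed among them. Assuming 10% and 10% gives 4 × 0.1 × 0.1 = 0.04, and assuming 30% and 50% gives 4 × 0.3 × 0.5 = 0.6. Neither share is in the documents. With plain addition and blanks meaning not examined, that shift would stay in the AOD domain and not reach the total.

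The conclusion rests on standard SAS handling of missing values and on reading the `*_ZERO` fields as contracture angles. The latter is inferred from the formulas; the SAP does not define the fields.

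**What to change.** Confirm the CRF convention for a blank `*_ZERO` field, then add one rule to SAP 7.4 that applies before both scores:

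1. If the other motion fields of a plane are recorded, set a blank `*_ZERO` to 0 for both ROM and AOD. If the plane was not examined, set ROM, AOD and total HHS to missing.
2. For leg length, require that at least one of none, longer or shorter is recorded. Set the unfilled alternatives to 0. If none of the three is recorded, set AOD to missing.
3. State that the total HHS is missing if any domain is missing.
4. Make the ROM bands non-overlapping, for example by starting the top band above 209.

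With blank set to 0 in both rules, the illustrative hip scores ROM 5, AOD 4 and HHS 100. With the plane treated as not examined in both, ROM, AOD and the total are all missing.

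The cost is a few lines of SAP text and derivation code. The downside is that some totals become missing instead of falsely complete.

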7.5 Baseline Data

Baseline characteristics with information available either at the preoperative or at the operative visit would be summarized using descriptive characteristics for continuous¹ or categorical² data but not only limited to the following variables:

CONFIDENTIAL AND PROPRIETARY

This document contains information that is confidential and proprietary to Smith & Nephew PLC and Smith & Nephew, Inc. and is intended for use only by Smith+Nephew and its manufacturer. It shall not be reproduced or copied in whole or in part, nor shall the contents be disclosed by any means without prior written permission from Smith+Nephew, nor shall anyone make any use of it that is contrary to the expressed or implied wishes of Smith+Nephew.

Statistical Analysis Plan

Multicenter Clinical Observation Using the Cementless Version of the
POLARSTEM™

Number: D10070
ST: 1133
Version: 1.0, 30-Nov-2021
Page: 15 of 19

- Body Mass Index (BMI)¹
- Operative data² (i.e. surgery access)
- Charnley classification²
- Physical activity²
- Medication²
- Previous ipsilateral surgeries²
- Local risk factors²
- General risk factors²
- Type of anesthesia²
- Surgery time¹
- Cup type²
- Cup size²
- Cup cemented²
- Stem size²
- Stem cemented²
- Head type²
- Head size²
- Neck length²
- Articulation²
- Operated Hip² (Right, Left, Bilateral).
- Fixation with additional screws²
- Tribological pairing²
- Primary diagnosis at enrollment²
- Intraoperative complications²
- Medical History² (i.e. general risk factors, diabetes, heart/circulatory, etc.)
- Local early postoperative complications²
- General early postoperative complications²

CONFIDENTIAL AND PROPRIETARY

This document contains information that is confidential and proprietary to Smith & Nephew PLC and Smith & Nephew, Inc. and is intended for use only by Smith+Nephew and its manufacturer. It shall not be reproduced or copied in whole or in part, nor shall the contents be disclosed by any means without prior written permission from Smith+Nephew, nor shall anyone make any use of it that is contrary to the expressed or implied wishes of Smith+Nephew.

Statistical Analysis Plan

Multicenter Clinical Observation Using the Cementless Version of the POLARSTEM™

Number: D10070
ST: 1133
Version: 1.0, 30-Nov-2021
Page: 16 of 19

7.6 Disposition Data

- This would be summarized as the number of subjects (and hips) that were prematurely terminated on-study would be presented as frequency (n) and percentage (%). The reasons for premature termination would also be presented. Additionally, a listing of all terminations would be presented.
- The disposition of subjects (and hips) would also be summarized as clinical follow-up of the subjects' hip from the operative through the 10 year postoperative follow-up. Information to be summarized in these tables would include but not only restricted to theoretically due, revisions, terminations, expected at visit and present at visit.

7.7 Protocol Deviations

The frequency of protocol deviations will be summarized along with the number of subjects experiencing each. Subjects with protocol deviations deemed as significant enough to exclude the subject from the Per Protocol analysis will be listed.

7.8 Measurement of Treatment Compliance

Not Applicable.

7.9 Multiplicity

Not Applicable.

7.10 Analysis of Primary Endpoint

- Short term, medium term and long term survival rates.
- Survival rates will be presented with a 95% confidence intervals at 3 months and at 1 year, 3 year, 5 year and 10 year postoperative time points from Kaplan-Meier product limit estimates.
- The revisions (by type of revision) will be tabulated and/or listed.

7.11 Analysis of Secondary Endpoints

- Harris Hip Score (HHS)

CONFIDENTIAL AND PROPRIETARY

This document contains information that is confidential and proprietary to Smith & Nephew PLC and Smith & Nephew, Inc. and is intended for use only by Smith+Nephew and its manufacturer. It shall not be reproduced or copied in whole or in part, nor shall the contents be disclosed by any means without prior written permission from Smith+Nephew, nor shall anyone make any use of it that is contrary to the expressed or implied wishes of Smith+Nephew.

Statistical Analysis Plan

Multicenter Clinical Observation Using the Cementless Version of the POLARSTEM™

Number: D10070
ST: 1133
Version: 1.0, 30-Nov-2021
Page: 17 of 19

- HOOS Score (Hip Dysfunction and Osteoarthritis Outcome Score), which includes the complete WOMAC Osteoarthritis Index
 - The different dimensions of and the overall HHS, and WOMAC from HOOS scores at all recorded time points and end of study will be summarized using mean, median, SD, minimum, and maximum. A paired sample t-test (or a non-parametric equivalent such as the Wilcoxon signed-rank test) will be used to test the difference between preoperative and postoperative scores.
- Radiological: At all recorded time points (from the perioperative through the 10 year postoperative follow-up), the following analyses would be carried out:
 - For general findings: At the acetabulum position, cranial migration (mm), medial migration (mm) and tilted angle would be summarized using descriptive characteristics for continuous variables; At the stem position, varus tilting, valgus tilting and sunken (mm) will be summarized using descriptive statistics for continuous variables; Integration in general/acetabulum, integration in general/stem and ectopic ossification will be summarized using descriptive statistics for categorical variables.
 - Within the cup and the stem (by zone): The number and percent of hips with osteolysis will be summarized; for seams (0mm, 1mm, 2mm &>2mm), atrophy (none, mild, moderate & severe) and hypertrophy (none, mild, moderate & severe) their frequencies (n) and percentages will be presented.

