1.3 Objectives

The goal of this multicenter clinical observation is to validate short-, mid-, and long-term outcome (efficacy and safety) of the POLARSTEM®.

Efficacy evaluations

- Evaluation of function, range of motion (ROM) and pain as assessed by Harris Hip Score, Hip disability and osteoarthritis outcome score (HOOS) [7, 8], an extension of the Western Ontario and McMaster Universities Osteoarthritis Index (WOMAC).
- Radiographic changes as defined by radiolucent lines, osteolysis, hypo- and hypertrophy, implant loosening or migration

Safety evaluations

- Intra- and perioperative device-related adverse events (AE) and complications up to discharge
- Postoperative AE up to 10 years

Long-term survivorship will be calculated according to Kaplan-Meier with stem revision due to any reason as endpoint.

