4.1 Primary Objective(s)

- Evaluation of function, range of motion (ROM), and pain as assessed by the Harris Hip Score (HHS), Hip disability and osteoarthritis outcome score (HOOS), an extension of the Western Ontario and McMaster Universities Osteoarthritis Index (WOMAC).
- Radiographic changes as defined by radiolucent lines, osteolysis, hypo- and hypertrophy implant loosening.

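### The HHS scoring table gives a summed arc of 209° two different scores, and the coarse 0–5 motion domain should be supplemented by the arcs in degrees that the SAP already derives

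*SAP*

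**What the plan says.** Protocol 1.3 lists among its efficacy evaluations: "Evaluation of function, range of motion (ROM) and pain as assessed by Harris Hip Score", together with the HOOS. SAP 4.1 repeats this under the primary objectives. Protocol 3.1 has range of motion recorded, as part of the HHS, before surgery and at each postoperative examination. SAP 5.2 lists the HHS as a secondary endpoint.

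The HHS table in SAP 7.4 defines three arcs, the first as "Flexion = FLEX+EXT-FLEX_ZERO" and the other two on the same pattern. The arcs carry no item score of their own. Their sum is converted to points as follows: 0–29 gives 0, 30–59 gives 1, 60–99 gives 2, 100–159 gives 3, 160–209 gives 4, and ≥ 209 gives 5.

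For the analysis, SAP 7.11 covers "The different dimensions of and the overall HHS", along with the WOMAC scores, at each recorded visit and at the end of the study. The summary statistics are mean, median, SD, minimum and maximum, and a paired t-test or Wilcoxon signed-rank test "will be used to test the difference between preoperative and postoperative scores". No section commits to a summary or test of the arcs in degrees. SAP 7.14 is a general provision for summarising other CRF data that may help interpretation; it names no motion variable.

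**The concern.** The table is an algorithm to be programmed. Where one input has two permitted outputs, the result depends on which row the code reads first, so two programmers could both follow the SAP and disagree.

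The second matter is information. Motion is named beside function and pain as something to evaluate over ten years, yet the only specified result for it is a six-level score worth 5 of the 100 HHS points. The table shows that sizeable changes in degrees can leave that score where it was, while a one-degree change across a boundary moves it by a full point. A reader of the final report could not say how many degrees patients gained or lost, although the program has to compute those degrees to obtain the score. The same section of the SAP reports cup migration, tilting and stem sinking as continuous measurements.

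**Working it through.** **Inputs.** All come from the HHS table in SAP 7.4: the six bands above, the item maxima and the stated maximum total of 100.

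**Reproducing the table's own totals.** Function items: 11 + 11 + 11 + 5 + 1 + 4 + 4 = 47, as stated. Total: pain 44 + function 47 + motion 5 + deformity 4 = 100, as stated. Motion is therefore 5/100 = 5% of the score.

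**Overlap.** Every whole-degree sum from 0 to 360 was checked against the printed bands. Exactly one value, 209, falls in two of them (4 and 5 points). The other boundaries are disjoint: 29/30, 59/60, 99/100, 159/160. The lower limits 30, 60, 100 and 160 are all multiples of ten, so a top band starting at 210 fits the pattern. Sums that are not whole numbers, such as 29.5, 59.5, 99.5 or 159.5, fall in no band; this matters only if angles are not recorded in whole degrees.

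**Band widths.** Number of whole-degree values = upper − lower + 1; largest change within a band = upper − lower.

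| Points | Band | Values | Largest change scoring 0 |
|---|---|---|---|
| 0 | 0–29 | 30 | 29° |
| 1 | 30–59 | 30 | 29° |
| 2 | 60–99 | 40 | 39° |
| 3 | 100–159 | 60 | 59° |
| 4 | 160–209 | 50 | 49° |
| 5 | ≥ 209 | open | no limit |

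A hip going from 100° to 159° gains 59° and 0 points; from 159° to 160° it gains 1° and 1 point. Because the sum combines three arcs, 59° is 59/3 ≈ 20° per arc if spread evenly. In the open band, a hypothetical fall from 280° to 215° (65°) scores 0.

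**How often a gain would be hidden.** The documents give no distribution of motion, so this can only be illustrated. Assume the starting sum is uniform over a range, with 209 scored as 5. The share with no score change is the number of starting values x for which score(x + d) = score(x), divided by all values in the range. For d = 30° and starts of 100–159, x must be at most 129, giving 30/60 = 50%.

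| Assumed starting range | 20° gain | 30° gain | 40° gain |
|---|---|---|---|
| 100–159° | 67% | 50% | 33% |
| 60–209° | 60% | 40% | 20% |
| 100–250° | 74% | 60% | 47% |

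The spread shows how much the answer depends on the assumed range.

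**After the correction.** With the top band starting above 209 and sums rounded to whole degrees, each sum from 0 upwards has exactly one score. In degrees, 100 to 159 reads as +59° and 159 to 160 as +1°.

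**The case against.** The strongest reply is that objective, endpoint and analysis agree. Both documents define motion as assessed through the HHS and HOOS, the SAP endpoint is the HHS, and SAP 7.11 analyses each HHS dimension. A reader might infer from the coarse scale that the SAP fails its own objective. The documents do not support that, and this reply stands in full. Coarse bands, the open top band and the 5% weight belong to the scoring that the SAP adopts, and wanting degrees as well is a request for more information.

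A reader might also infer that motion scores will sit at the ceiling and that the report will therefore tend to show motion as maintained. No motion data appear in the documents, so this is conjecture. Banding hides gains as well as losses, a loss that crosses a boundary does lower the domain mean, and a median and a signed-rank test are available beside the mean and t-test.

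It can be said, finally, that SAP 7.14 leaves room to tabulate the arcs, and that the table shells listed in SAP 2, which are not among the documents reviewed, may already do so. Room is not a commitment, and neither SAP 7.14 nor SAP 7.1 names the arcs. None of these replies touches the 209° overlap.

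**Conclusion.** Two modest points hold. The 209° overlap is a definite error in a scoring rule. It is worth 1 point of the motion domain and of total HHS for hips at exactly that sum, and is expected to be rare. Separately, the specified motion result is consistent with the objective but coarse: changes of up to 59° within a band, and any change between sums above 209°, score zero. Reporting degrees would be more informative at almost no cost.

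The zero-change limits follow from the table alone. The percentages above rest on an assumed uniform start and should not be read as estimates for this cohort. One might go further and make degrees the motion result in place of the domain score. That is not warranted: the domain analysis is prespecified, it matches the objective, and SAP 6.3 records that a 5-year interim analysis has already been reported. The primary survival endpoint, the sample size and the other HHS domains are unaffected.

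**What to change.** 1. In the SAP 7.4 table, change the top motion band from ≥ 209 to > 209, and state that the summed arc is rounded to whole degrees before banding.
2. In SAP 7.11, add a supplementary analysis, labelled as such: by-visit summaries of the flexion, movement and rotation arcs and their sum in degrees, with the mean paired change from the preoperative value and its 95% confidence interval.
3. Leave the HHS motion-domain analysis as it is.

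The cost is a few words in the SAP and a few extra table rows, from variables that the scoring already requires. There is no new data collection, no patient burden and no change to sample size. If analysis has already begun, the degree summaries should be identified as added afterwards.

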Multicenter Clinical Observation Using the Cementless Version of the POLARSTEM®

SUMMARY	2
1 STUDY OBJECTIVES	3
1.1 Background	3
1.2 The POLARSTEM®.....	3
1.3 Objectives	4
2 STUDY DESIGN	5
2.1 Patient selection	5
2.2 Sample size consideration.....	6
2.3 Study duration	6
2.4 Pseudonymisation of patient identifiable information.....	6
3 STUDY METHOD	7
3.1 General	7
3.2 Postoperative rehabilitation	7
3.3 Follow-up.....	7
3.4 Complications/adverse events/lost-to follow-up.....	8
3.5 Patient recruitment	8
4 DESCRIPTION OF THE DEVICES	9
4.1 Implants	9
4.2 Instruments	9
5 ETHICAL AND LEGAL ASPECTS	10
5.1 Ethical aspects	10
5.2 Legal aspects.....	10
6 PARTNERS	11
6.1 Study sponsor and monitor	11
6.2 Investigators	11
6.3 Publication policy	12
7 SIGNATURE	13
8 REFERENCES	14

SUMMARY

Objective: Validation of the POLARSTEM® as state-of-the-art implant in terms of radiographic, clinical performance and long-time survivorship.

Study design: Prospective study

Study population: Total of 225 patients in 3 different sites

Intervention (if applicable): Implantation of a total hip prosthesis

Main study parameters/endpoints: Radiographic: radiolucent lines, osteolysis, hypo- or hypertrophy; implant loosening or migration; Clinical: Harris Hip Score and HOOS Score

Nature and extent of the burden and risks associated with participation, benefit and group relatedness: Patients will benefit without restriction from their total hip prosthesis. Patients enrolled in this study will receive the same operation and the same follow-up treatments as patients not enrolled. Therefore, no additional risks are expected.

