3 STUDY METHOD

3.1 General

Patients' pre-operative status, surgical procedure as well as clinical and radiological outcome will be documented by means of Case Report Forms (CRFs) that are provided by the study sponsor. CRFs will be filled in the investigator or specially assigned hospital personnel who have been trained for the study. Completed CRFs are faxed from the site to the sponsor immediately upon completion. Case Report Forms are the basis for further data evaluation.

Pain, function, gait, range of motion (HHS) and radiographic status determinations are made pre-operatively and at each post-operative examination. Radiographic analysis will be done on standard AP and lateral view X-rays.

Pre-and postoperative HOOS questionnaires are filled in by the patients themselves. Patients must have the possibility to complete the forms on their own, without any external influence. This means patients should have the possibility to take the questionnaire home and return it to the hospital at a later date.

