5.2 Secondary Endpoints

- Harris Hip Score (HHS)
- HOOS Score (Hip Dysfunction and Osteoarthritis Outcome Score), which includes the complete WOMAC Osteoarthritis Index
- Radiological: radiolucent lines, osteolysis, hypo- and hypertrophy of the cortex, loosening of the implant or migration

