- ❖ **Revision:** Binary indicator variable for presence of revision
- ❖ **Adverse event:** Binary indicator for whether a patient experiences at least one adverse event.
- ❖ **Scores (HHS and WOMAC from HOOS):** The global scores or scores under each dimension of the questionnaire under consideration will be determined per specific scoring instructions for each questionnaire.
 - ❖ Harris Hip Score (HHS)
 - ❖ Algorithms used for scoring each of the 10 items (components) of the HHS as well as the domains (pain, function, AoD and ROM) of the HHS and total HHS are presented below:
 - ❖

CONFIDENTIAL AND PROPRIETARY

This document contains information that is confidential and proprietary to Smith & Nephew PLC and Smith & Nephew, Inc. and is intended for use only by Smith+Nephew and its manufacturer. It shall not be reproduced or copied in whole or in part, nor shall the contents be disclosed by any means without prior written permission from Smith+Nephew, nor shall anyone make any use of it that is contrary to the expressed or implied wishes of Smith+Nephew.

Statistical Analysis Plan

Multicenter Clinical Observation Using the Cementless Version of the
POLARSTEM™

Number: D10070
ST: 1133
Version: 1.0, 30-Nov-2021
Page: 11 of 19

Harris Hip Score (HHS) scores per item and domain			
Item	Original Response	Likely scores per Item	Domains (Range of Scores)
Pain	None or ignores it	44	Pain Domain (0 to 44)
	Slight, minimal, no compromise in activities	40	
	Mild pain, no effect on average activities, rarely moderate pain with unusual activity; may take aspirin	30	
	Moderate pain; tolerable but makes concessions to pain. Some limitation of ordinary activity or work. May require occasional pain medication stronger than aspirin	20	
	Marked pain, serious limitation of activities	10	
	Totally disabled, crippled, pain in bed, bedridden	0	
Limp	None	11	Function Domain (0 to 47) {Sum of all items within subdomain}
	Slight	8	
	Moderate	5	
	Severe	0	
Support	None	11	
	Single cane for long walks	7	
	Single cane most of the time	5	
	One crutch	3	
	Two canes	2	
	Two crutches or not able to walk	0	
Distance walked	Unlimited	11	
	Six blocks	8	
	Two or three blocks	5	
	Indoors only	2	
	Bed and chair only	0	
Sitting	Comfortably in ordinary chair	5	
	On a high chair for 30 minutes	3	
	Unable to sit comfortably in any chair	0	

CONFIDENTIAL AND PROPRIETARY

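### HOOS is a declared endpoint, but the SAP scores, summarises and tests only its WOMAC component and does not declare the narrowing

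*SAP*

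**What the plan says.** Both documents name HOOS as something to be evaluated:

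- Protocol, Summary, main parameters: "Clinical: Harris Hip Score and HOOS Score".
- Protocol 1.3, efficacy evaluations: "Hip disability and osteoarthritis outcome score (HOOS) [7, 8], an extension of the Western Ontario and McMaster Universities Osteoarthritis Index (WOMAC").
- Protocol 3.1: "Pre-and postoperative HOOS questionnaires are filled in by the patients themselves". Table 1 in Protocol 3.3 schedules HHS/HOOS before surgery and at every follow-up.
- SAP 4.1, among the primary objectives: "Hip disability and osteoarthritis outcome score (HOOS), an extension of the Western Ontario and McMaster Universities Osteoarthritis Index (WOMAC").
- SAP 5.2, as a secondary endpoint: "HOOS Score (Hip Dysfunction and Osteoarthritis Outcome Score), which includes the complete WOMAC Osteoarthritis Index".

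The sections that say what will be computed are narrower:

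- SAP 7.4 opens its scoring entry with "Scores (HHS and WOMAC from HOOS").
- After the Harris table, the same section continues: "For the WOMAC from HOOS, algorithms used in deriving the pertinent endpoints are as presented below". The item table and the transformation to a 0 to 100 scale that follow concern WOMAC stiffness, pain and function only.
- SAP 7.11 repeats the HOOS endpoint as a bullet title, but the analysis beneath it covers "The different dimensions of and the overall HHS, and WOMAC from HOOS scores at all recorded time points". A paired t-test or its non-parametric equivalent then compares scores before and after surgery.

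SAP 7.15 records one matter, the inconsistent sample-size statements in the protocol.

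**The concern.** The documents themselves present HOOS as the larger instrument: it extends WOMAC and includes it. A WOMAC score is then a score on part of HOOS. A programmer who follows 7.4 and 7.11 exactly would produce Harris and WOMAC tables, and no HOOS subscale or other HOOS score would exist to tabulate.

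At stake is the match between the declared patient-reported endpoint and the reported one. Results for a component could appear under the HOOS title, and a reader could not see whether the rest of the questionnaire agreed with it. If the narrowing was intended, the plan gives neither a statement of it nor a reason.

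**Working it through.** **1. Reproduce the SAP's own figure.** SAP 7.4 scores each item from 0 to 4 and states a total raw WOMAC range of 0 to 96. The maximum for each domain is the number of items × 4:

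- Stiffness, S1 to S2: 2 × 4 = 8
- Pain, P1 to P5: 5 × 4 = 20
- Function, A1 to A17: 17 × 4 = 68
- Items: 2 + 5 + 17 = 24
- Total: 8 + 20 + 68 = 96

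Each domain maximum and the total agree with the SAP. The 24 items account for the whole stated WOMAC total, so no other HOOS item enters the score.

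**2. Follow HOOS through the plan.**

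| Step | Where | HOOS | WOMAC component |
|---|---|---|---|
| Objective or main parameter | Protocol Summary, 1.3; SAP 4.1 | named | named as what HOOS extends |
| Collection | Protocol 3.1, 3.3 | questionnaire at each scheduled time point | within HOOS |
| Endpoint | SAP 5.2 | named | named as included |
| Derivation | SAP 7.4 | none beyond WOMAC | 24 items, raw and transformed |
| Per-visit summary | SAP 7.11 | title only | yes |
| Paired pre/post test | SAP 7.11 | none beyond WOMAC | yes |
| Declared change | SAP 7.15 | none | none |

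**3. Look for a clause that fills the gap.**

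- SAP 7.4 refers to each questionnaire's own scoring instructions. That sentence sits under an entry restricted to HHS and WOMAC from HOOS, so it does not add HOOS subscales.
- SAP 7.1 promises summaries of outcome variables at all recorded times. It defines no HOOS score to summarise.
- SAP 7.14 allows other CRF data to be summarised where this helps interpretation. It is discretionary and applies to data with no planned analysis, so a named endpoint should not depend on it.

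**4. What cannot be computed.** Neither document gives the number of HOOS items or subscales. The share left unscored is therefore unknown.

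**The case against.** The strongest reply is that the endpoint is reported in substantial part. The WOMAC component is fully scored, summarised at every recorded time point and tested. The objective concerns function, range of motion and pain. WOMAC supplies pain and function scores, and the Harris score supplies pain, function and range-of-motion domains. Each construct named in the objective therefore has a planned analysis. This stands, and it rules out two stronger readings that a reader might infer: that the HOOS endpoint would go wholly unreported, and that the study could not address its objective. What is missing is the remaining content of the named instrument.

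The TFL shells that SAP 2 lists as a related document are not available here and may contain HOOS tables. That is possible, but a shell would still need a score definition, and the SAP gives none.

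A reader might size the loss by multiplying the 225 patients by the six scheduled time points. That product is a ceiling on the schedule. Protocol 2.2 allows for 30% drop-out, and SAP 7.4 says the study was terminated early. It also says nothing about how much of each questionnaire goes unscored.

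A reader might also infer that the subset was chosen after the interim results were seen, because SAP 6.3 says the 5-year analyses had already been reported and this version is dated 30 November 2021. The documents do not say which HOOS-derived scores the interim used or when WOMAC scoring was settled, so they do not support that inference.

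**Conclusion.** The point holds as a mismatch between the declared endpoint and the planned analysis. HOOS is a main parameter in the protocol and a secondary endpoint in SAP 5.2. The scoring and analysis rules reach only its 24-item WOMAC component, and SAP 7.15 does not declare the narrowing. This is more than missing detail, because the stated rule, followed exactly, gives no HOOS score beyond WOMAC.

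The consequence is moderate. The SAP's primary endpoint is survival (SAP 5.1), which is unaffected, and no sample size or success criterion depends on HOOS. The change should be made, but it does not threaten the main result.

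The conclusion rests on one reading: that HOOS contains something beyond WOMAC. This follows from the documents' own description of HOOS as an extension of WOMAC that includes all of it. How much more it contains, and on what subjects, is not stated.

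**What to change.** Either of two changes removes the inconsistency.

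1. **Analyse HOOS as declared.** In SAP 7.4, add derivation of the HOOS subscale scores by the instrument's scoring instructions, cited or appended because the documents do not contain them, with a stated rule for unanswered items. In SAP 7.11, add these scores to the per-visit summaries and the paired pre/post test. Keep WOMAC from HOOS as an additional score.
2. **Declare the narrowing.** If the sponsor intends WOMAC only, name WOMAC from HOOS as the endpoint in SAP 5.2, and record and justify the change in SAP 7.15.

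The first option costs SAP wording and a few tables, from questionnaires that the protocol already collects. It also adds some secondary tests. SAP 7.9 provides no multiplicity adjustment, so their p-values should be read as descriptive. The second option costs wording only, but leaves the remaining HOOS content without a planned analysis.
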